### 6.3.2 Dose Re-escalation After Resolution of Adverse Drug Reactions

Avapritinib and regorafenib doses may be re-escalated from the reduced dose level to the immediate previously administered dose level if any of the following criteria are met:

- All  $\geq$  Grade 2 non-hematologic (other than CNS toxicities) have recovered to  $<$  Grade 2 for at least 2 weeks.
- All  $\geq$  Grade 3 hematologic toxicities have recovered to  $\leq$  Grade 2 and are manageable with supportive therapy.
- All  $\geq$  Grade 2 CNS toxicities have recovered to  $\leq$  Grade 1 and are manageable with supportive therapy.

Patients may receive step-wise avapritinib dose re-escalations up to 300 mg QD (eg, 100 mg QD to 200 mg QD to 300 mg QD) if the above criteria continue to be met.

Patients may receive step-wise regorafenib dose escalations up to 160 mg QD (eg, 80 mg QD to 120 mg QD to 160 mg QD) if the above criteria continue to be met.

A patient should be treated and tolerate therapy well for at least 1 cycle at each higher dose level before the dose is escalated again. In no circumstances should a patient receive a dose higher than 300 mg QD.

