### **6.3.1 Dose Modification Recommendations for Adverse Events**

Dose modification guidelines are summarized for avapritinib in [Table 1](#), and for regorafenib in [Appendix 2](#). These guidelines should be followed by clinical Investigators; however, for an individual patient, dose interruptions, reductions, and treatment discontinuation should also be based on the clinical circumstance. Deviation from these guidelines must be documented and communicated with the sponsor.

Adverse events are to be graded according to NCI CTCAE version 5.0. When the observed toxicity has resolved to  $\leq$  Grade 2 or returned to baseline, the investigator may resume dosing if clinically indicated. Guidance for re-escalation after resolution of adverse drug reactions is provided in [Section 6.3.2](#).

Avapritinib dose reductions to below 100 mg QD are not permitted (see [Table 1](#)), and regorafenib dose reductions to below 80 mg QD are not permitted (See [Appendix 2](#)). If a patient requires dose reduction below these dose levels, study treatment should be discontinued.

Doses may be interrupted for study-drug related toxicities for up to 56 days (8 weeks). In general, if a study drug-related toxicity does not resolve to  $\leq$  Grade 2 or has not returned to baseline after dose interruption for more than 56 days, the patient must be discontinued from study treatment unless after discussion with the medical monitor, resumption of treatment is considered to be in the best medical interest of the patient, and this is documented in writing. Additionally, the Sponsor's medical monitor must be contacted if

an AE deemed unrelated to treatment requires a dose interruption for more 56 days; a longer recovery period is permitted with written approval by the Sponsor.

During dose interruptions, study sites should continue to observe the study schedule as planned.

Once adverse drug reactions have resolved after the guidelines below are followed, Investigators are encouraged to re-escalate the dose of study drug as described in [Section 6.3.2](#).

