**18.2 Appendix 2**

**PRESPECIFIED DOSE MODIFICATIONS FOR ADVERSE EVENTS  
RELATED TO REGORAFENIB**

**Prespecified dose modifications for adverse events related to study drug excluding hand–foot skin reaction, hypertension, and aspartate aminotransferase (AST), alanine aminotransferase (ALT), or bilirubin increases**

National Cancer Institute Common Terminology Criteria for Adverse Events, version 5.0 (NCI-CTCAE v5.0) Grade	Dose Interruption	Dose Modification a	Dose for Subsequent Cycles
Grade 0–2	Treat on time	No change	No change
Grade 3	Delay until $\leq$ Grade 2 b	Reduce by 1 dose level c	If toxicity remains $\leq$ Grade 2, dose re-escalation can be considered at the discretion of the treating investigator. If dose is re-escalated and toxicity ( $\geq$ Grade 3) recurs, institute permanent dose reduction
Grade 4	Delay until $\leq$ Grade 2 b	Reduce by 1 dose level. Permanent discontinuation can be considered at treating investigator's discretion	

a Not for alopecia, non-refractory nausea/vomiting, non-refractory hypersensitivity, and asymptomatic laboratory abnormalities.

b Patients requiring a delay of  $>$  56 days should discontinue protocol therapy.

c Dose level 0 = 160 mg, dose level –1 = 120 mg, dose level –2 = 80 mg.

Source: (Demetri et al, 2013b)

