**Prespecified Dose Modifications for Treatment-related Hypertension**

NCI-CTCAE v5.0 Grade	Definition	Antihypertensive therapy	Study drug dosing
Grade 1	Systolic blood pressure (BP) 120– 139 mmHg or diastolic BP 80-89 mmHg	None	Continue study drug Consider increased blood pressure monitoring
Grade 2	Systolic BP 140–159 mmHg or diastolic BP 90–99 mmHg if previously within normal limits; change in baseline medical intervention indicated; recurrent or persistent ( $\geq 24$ h); or Symptomatic increase by $> 20$ mmHg (diastolic) or to $> 140/90$ mmHg; monotherapy indicated initiated	Treat to achieve diastolic BP $\leq 90$ mmHg If BP previously within normal limits, start antihypertensive monotherapy If patient already on antihypertensive medication, titrate dose up	Continue study drug If symptomatic, hold study drug until symptoms resolve and diastolic BP $\leq 90$ mmHg a On resuming study drug, continue at same dose level
Grade 3	Systolic BP $\geq 160$ mmHg or diastolic BP $\geq 100$ mmHg; Medical intervention indicated; More than one drug or more intensive therapy than previously used indicated	Treat to achieve diastolic BP $\leq 90$ mmHg — Start antihypertensive medication and/or — Increase current antihypertensive medication and/or — Add additional antihypertensive medications	Hold study drug until diastolic BP $\leq 90$ mmHg and, if symptomatic, symptoms resolve On resuming study drug, continue at same dose level If BP is not controlled with addition of new or more intensive therapy, reduce study drug by one dose level b,c If Grade 3 hypertension recurs despite study drug dose reduction and antihypertensive therapy, reduce study drug by one additional dose level b,d
Grade 4	Life-threatening consequences (e.g., malignant hypertension, transient or permanent neurological deficit, hypertensive crisis) Urgent intervention indicated		Discontinue treatment

a Patients requiring a delay of  $> 4$  weeks should discontinue protocol therapy.b Dose level 0 = 160 mg, dose level -1 = 120 mg, dose level -2 = 80 mg.c If blood pressure remains controlled for at least one full cycle, study drug dose re-escalation is permitted at the investigator's discretion.d Patients requiring  $>2$  study drug dose level reductions (ie, a reduction that would result in a study drug dose  $< 80$  mg) should discontinue protocol therapy

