**Prespecified Dose Modifications for Treatment-related Increases in ALT and/or AST and/or Bilirubin**

NCI-CTCAE v5.0 Grade	1st occurrence	Restart	Reoccurrence
Baseline Grade 0→Grade 1 or Baseline Grade 1→Grade 2	Give study drug on time Check AST, ALT and bilirubin twice weekly for 2 weeks then weekly for at least 4 weeks		Give study drug on time Check AST, ALT and bilirubin twice weekly for 2 weeks then weekly for at least 4 weeks
Baseline Grade 0→Grade 2	Delay study drug until ≤ Grade 1 Check AST, ALT, and bilirubin twice weekly	Reduce study drug by 1 dose level a Check AST, ALT, and bilirubin twice weekly for 2 weeks then weekly for at least 4 weeks b	Discontinue study drug c
Baseline any Grade→Grade 3	Delay study drug until ≤ Grade 1 if baseline was Grade 0 or 1 or until Grade 2 if baseline was Grade 2 Check AST, ALT, and bilirubin twice weekly If ALT or AST >8× upper limit of normal, with concomitant rise in bilirubin (of any degree) versus previous bilirubin values, consider permanent discontinuation of study drug at first occurrence c	Reduce study drug by 1 dose level a Check AST, ALT, and bilirubin twice weekly for 2 weeks then weekly for at least 4 weeks b	Discontinue treatment c
Baseline any Grade→Grade 4	Discontinue treatment c		

a Dose level 0 = 160 mg, dose level -1 = 120 mg, dose level -2 = 80 mg.

b If all values remain stable for two full cycles, study drug dose re-escalation may be considered at the discretion of the investigator. After re-escalation AST, ALT, bilirubin should be checked twice weekly for 2 weeks then weekly for at least 4 weeks.

c In case of discontinuation, check AST, ALT, and bilirubin twice weekly for 2 weeks then weekly until recovery to baseline.

**18.3 Appendix 3****EXCLUDED MEDICATIONS AND FOODS FOR PATIENTS  
RECEIVING AVAPRITINIB**

Strong CYP3A4 Inhibitors	Strong CYP3A4 Inducers	Moderate CYP3A4 Inducers
Boceprevir	Carbamazepine	Bosentan
Clarithromycin	Phenytoin	Efavirenz
Cobicistat	Rifampin	Etravirine
Conivaptan	St. John's Wort	Modafinil
Grapefruit, grapefruit juice	Phenobarbital	Dabrafenib
Indinavir		
Itraconazole		
Ketoconazole		
Lopinavir		
Nefazodone		
Nelfinavir		
Posaconazole		
Ritonavir		
Saquinavir		
Telaprevir		
Telithromycin		
Voriconazole		

Abbreviations: CYP3A4 = cytochrome P450 3A4.

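### Section 6.3.2 and Appendix 2 set different re-escalation conditions for the same regorafenib toxicities, chiefly liver and hypertension, and the protocol does not clearly say which governs.

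*Protocol*

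**What the plan says.** Protocol Section 6.3.1 refers regorafenib dose changes to Appendix 2, says those tables are to be followed, and requires departures to be documented and reported to the sponsor. Going back up in dose is then covered twice.

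- **Section 6.3.2** covers both drugs: "Avapritinib and regorafenib doses may be re-escalated from the reduced dose level to the immediate previously administered dose level" if any of three recovery criteria is met. The non-hematologic, non-CNS criterion is that all events of Grade 2 or worse have come down to below "Grade 2 for at least 2 weeks". The section lists the regorafenib steps (80, 120, 160 mg). For repeated steps it adds: "A patient should be treated and tolerate therapy well for at least 1 cycle at each higher dose level before the dose is escalated again".
- **Appendix 2, liver table, footnote b:** "If all values remain stable for two full cycles, study drug dose re-escalation may be considered at the discretion of the investigator".
- **Appendix 2, hypertension table, footnote c:** "If blood pressure remains controlled for at least one full cycle, study drug dose re-escalation is permitted".
- **Appendix 2, general table:** re-escalation can be considered if the toxicity stays at Grade 2 or lower, with no minimum time. If toxicity of Grade 3 or worse "recurs, institute permanent dose reduction".

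Section 6.3.1 also names Section 6.3.2 as the source of re-escalation guidance, and adds: "Investigators are encouraged to re-escalate the dose of study drug as described in" that section.

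**The concern.** Raised liver enzymes and hypertension are non-hematologic, so a patient reduced for either falls under both texts. Section 6.3.2 makes no exception for them, and Appendix 2 does not refer back to Section 6.3.2. A site could reasonably take Appendix 2 as the rule for going down and Section 6.3.2 as the rule for going up.

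Two things are at stake. The first is safety: the protocol's background (Section 1.1.2) links regorafenib to severe liver injury, including fatal cases, and liver toxicity is where the stated waiting times differ most. The second is deviation handling. A site that steps up two weeks after recovery from a liver event follows Section 6.3.2 but departs from Appendix 2. Whether that must be reported as a departure is undefined. The SAP classes deviations as major or minor (Section 3.6) and removes patients with specified major ones from the Per Protocol population (Section 2.3).

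**Working it through.** The plan states no figure to reproduce. The check sets the texts side by side and converts the waiting times to days. A regorafenib cycle is 28 days (Section 6.3).

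| Event | Section 6.3.2 | Appendix 2 |
|---|---|---|
| ALT/AST/bilirubin | below Grade 2 for 2 weeks = 14 days | stable for 2 cycles = 2 × 28 = 56 days |
| Hypertension | below Grade 2 for 2 weeks = 14 days | controlled for 1 cycle = 28 days |
| General, non-hematologic, non-CNS | below Grade 2 for 14 days | stays at Grade 2 or lower, no duration |

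**1. Both clocks start at recovery.** Liver: 56 − 14 = 42 days apart (56/14 = 4-fold). Hypertension: 28 − 14 = 14 days apart (28/14 = 2-fold).

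**2. Liver clock in Appendix 2 starts at restart.** Appendix 2 does not say when its two cycles begin. Suppose they run from restart at the reduced dose, r days after recovery. After a rise to Grade 3, restart needs at most "Grade 1 if baseline was Grade 0 or 1 or until Grade 2 if baseline was Grade 2"; a rise from Grade 0 to Grade 2 likewise needs Grade 1 or lower. With baseline Grade 0 or 1, the Section 6.3.2 clock has therefore started by the time of restart. The earliest step up, counted from recovery, is max(14, r) under Section 6.3.2 and r + 56 under Appendix 2. The gap is r + 56 − max(14, r):

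- r = 0: 56 − 14 = 42 days
- r = 7: 63 − 14 = 49 days
- r = 14 or more: 56 days

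**3. The one-cycle sentence in Section 6.3.2.** It applies to a further step after a re-escalation. It does not set the wait before the first step, so it does not close the gap.

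**4. Cases where Section 6.3.2 is stricter.** With baseline Grade 2 liver values, Appendix 2 allows restart at Grade 2. Values that stay there for two cycles meet footnote b but not the below-Grade-2 criterion. For hypertension, the Appendix 2 target is a diastolic pressure of 90 mmHg or less. A patient at that target with systolic pressure still at 140–159 mmHg, a range the same table lists under Grade 2, could count as controlled and still fail Section 6.3.2.

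**5. General toxicity.** An event that settles at Grade 2 qualifies under Appendix 2 but not under the non-hematologic criterion of Section 6.3.2. For hematologic events both texts use Grade 2 or lower, so the threshold differs only outside that class.

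**The case against.** The best defense is that Section 6.3.1 implies an order. Its sentence encouraging re-escalation opens by supposing that the reaction has resolved with the guidelines followed, and those guidelines include Appendix 2. Section 6.3 and the line after Table 1 also route regorafenib events to Appendix 2. On this reading a site satisfies Appendix 2 first and then turns to Section 6.3.2. The reading is possible, but the clause concerns how the reaction was brought to resolution. It does not say that the re-escalation footnotes must also be met, and Section 6.3.1 separately names Section 6.3.2 as the re-escalation guidance.

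Second, both texts are permissive, so waiting for the later date breaches neither. That is true, but no passage makes the conditions cumulative, and a site using Section 6.3.2 alone would not know it had departed from Appendix 2.

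Third, Appendix 2 limits the liver risk: it requires twice-weekly tests for two weeks after re-escalation, then weekly tests for at least four weeks, and it calls for discontinuation if a rise that led to a reduction reoccurs. This stands as mitigation, but it does not settle the timing.

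A reader might also count the hand-foot and recurrence rules as contradictions. The documents do not support that. Grade 0–1 for hand-foot reaction is the same as below Grade 2, and Section 6.3.2 only adds a duration where Appendix 2 is silent. The permanent reduction on recurrence appears in Appendix 2 alone and is compatible with Section 6.3.2.

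**Conclusion.** The inconsistency is real for liver toxicity and hypertension, with a smaller mismatch in the grade threshold for general non-hematologic toxicity. With both clocks starting at recovery, a patient could step up at day 14 under Section 6.3.2, against day 56 (liver) or day 28 (hypertension) under Appendix 2. The liver gap is 42 days on that assumption and 42 to 56 days if the two cycles run from restart. These figures assume that no other event of Grade 2 or worse is unresolved and that the Section 6.3.2 criterion applied is the one for the patient's own toxicity class.

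Three stronger conclusions are tempting but not supported:

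- **That Section 6.3.2 is always the looser text.** The baseline Grade 2 liver case and the systolic-pressure case show otherwise.
- **That the affected group can be sized from the rates in Section 4.2.** Applied to 230 patients, 67% with hand-foot reaction gives 230 × 0.67 ≈ 154, and 59% with hypertension gives 230 × 0.59 ≈ 136. Those rates are not restricted to events that lead to a dose reduction; hand-foot reaction is outside the conflict, and Appendix 2 reduces the dose for hypertension only when a Grade 3 event is not controlled by added therapy. No rate is given for liver-related reductions.
- **That the conflict biases PFS.** Nothing in the documents shows that optional re-escalation some weeks earlier or later, in a subset of unknown size, shifts the comparison. The SAP reports relative dose intensity and dose modifications by arm (Sections 4.5.5 and 4.5.6), so a difference in delivered dose would be visible.

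**What to change.** The sponsor's medical team should reconcile Section 6.3.2, the cross-reference in Section 6.3.1 and Appendix 2 so that each regorafenib toxicity class has a single governing re-escalation condition. Alternatively, the protocol should state which text prevails, or that both must be met. Where a waiting time is kept, the text should say when the clock starts. This review takes no view on which condition is right.

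The cost is wording in two sections and the relevant Appendix 2 cells and footnotes, plus a clarification letter to sites. Protocol Section 13 requires permanent changes to go through an amendment with IRB/IEC approval, so the wording can travel with the next one. No new data, visits or procedures are needed.

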Treatment with avapritinib has been well tolerated in patients with GIST. Most AEs have been Grade 1 or 2 in intensity, with the most common ( $\geq 25\%$ ) including nausea (56%), fatigue (53%), periorbital edema (43%), vomiting (41%), peripheral edema (34%), anemia (31%), diarrhea (31%), cognitive effects (consisting of multiple similar AEs aggregated into a single category [30%]), increased lacrimation (30%), and decreased appetite (28%). There were no DLTs until the 600 mg dose cohort was reached and DLTs were noted in 2 patients: 1 patient experienced Grade 2 hypertension, Grade 2 rash, and Grade 2 memory impairment; the other patient experienced Grade 2 hyperbilirubinemia. The maximum tolerated dose was determined to be 400 mg QD.

Overall, 49 patients discontinued avapritinib treatment. Six patients discontinued due to AEs, 40 patients discontinued due to disease progression, and 3 patients discontinued avapritinib due to patient's decision.

The single dose (Cycle 1 Day 1; C1D1) and steady state (Cycle 1 Day 15; C1D15) pharmacokinetics of avapritinib have been evaluated in Study BLU-285-1101. Preliminary unaudited PK data from the 11 April 2018 datacut are presented. After administration of single oral doses of avapritinib ranging from 30 to 400 mg avapritinib, the median time to peak concentration ( $T_{max}$ ) ranged from 2 to 4 hours postdose, and the mean plasma elimination half-life of avapritinib ranged from 35 hours to 57 hours. After a single dose and repeat dosing of avapritinib, systemic exposure was dose proportional over the dose range of 30 mg to 400 mg QD. The steady state (C1D15) geometric mean  $C_{max}$  (%CV) of avapritinib at doses of 300 mg QD and 400 mg QD was 774 ng/mL (49.4%) and 1009 ng/mL (50.9%), respectively, and the corresponding area under the plasma concentration-time curve ( $AUC_{0-\tau}$ ) was 14074 h•ng/mL (45.1%) and 20298 h•ng/mL (41.5%), respectively. The mean accumulation ratio after repeat dosing of avapritinib (dose range: 30 – 400 mg QD) was 3.4 – 5.2. Based on the data collected thus far, and the exposures required for antitumor activity in GIST patient-derived xenograft models (Figure 2), systemic exposure at 300 mg QD - 400 mg QD is predicted to provide broad coverage of the primary (eg, exon 11) and secondary KIT (eg, exon 11/17 and exon 11/13) mutations.

[figure not shown]
**Figure 2: Clinical Exposure of Avapritinib Reaches Levels Projected to be Efficacious Across Multiple KIT-mutant Genotypes**

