**Table 1: Dose Modification and Re-escalation Guidelines for Avapritinib-Related Toxicity**

Toxicity	Modification
General	
Grade 1 or Grade 2	
 
No dose modification required
 

Grade 3 - 4	
 
Occurrence: Hold until event is <math>\leq</math> Grade 2, or has returned to baseline, and then resume by reducing the dose by 100 mg less than the current dose 
 

 
 
 
Occurrence at 100 mg: Discontinue avapritinib 
 

 
 
 

Cognitive or Mood Effects	
Grade 1 with only minor impairment	No dose modification required
Grade 1, other than minor impairment	
 
Interrupt dosing for 7 days, and resume dosing without dose reduction
 
The dosing interruption may be repeated if the impairment continues to worsen after resuming dosing; however, repeated dosing interruption is at the discretion of the investigator, and should be balanced with the need to treat the underlying GIST
 

Grade 2	
 
Interrupt dosing for a minimum of 7 days
 
Resume dosing with a dose reduction of 100 mg when the cognitive effect has improved to Grade 1 or less, or still at Grade 2, if continued treatment is considered in the best medical interest of the patient due to the underlying GIST
 
If the patient is already receiving a dose of 100 mg QD, and continued treatment is considered in the best medical interest of the patient due to the underlying GIST, treatment may be resumed at 100 mg
 

Grade 3-4	
 
Interrupt dosing for a minimum of 14 days
 
Resume dosing with a dose reduction of 100 mg when the cognitive effect has improved to Grade 1 or less, or when it has improved to Grade 2, if continued treatment is considered in the best medical interest of the patient due to the underlying GIST
 
Occurrence at 100 mg: Discontinue avapritinib
 

Intracranial Bleeding	
Grade 1	
 
Interrupt dosing for a minimum of 7 days, and re-image the brain
 

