	
 
Resume dosing without dose reduction, if the bleed is stable or improving, and continued treatment is considered in the best medical interest of the patient due to the underlying GIST
 

Grade 2	
 
Interrupt dosing for a minimum of 14 days and re-image the brain
 
Resume dosing with a dose reduction of 100 mg when the intracranial bleeding has improved to Grade 1 or less, or still at Grade 2, if continued treatment is considered in the best medical interest of the patient due to the underlying GIST
 
Occurrence at 100 mg: Discontinue avapritinib
 

Grade 3-4	
 
Discontinue avapritinib
 

Abbreviations: CNS = central nervous system; GIST = gastrointestinal stromal tumor; QD = once daily.

 Changes in cognition, memory, attention, mood, or speech (thought to originate in the CNS).

 If avapritinib treatment is resumed after interruption for a cognitive or mood effect, or for an intracranial bleeding event, the investigator must document in writing that resuming avapritinib treatment was considered to be in the best medical interest of the patient.

For regorafenib, dose modification is described in [Appendix 2](#).

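### Read literally, Protocol 6.3.2 lets the first avapritinib re-escalation step go ahead on a non-CNS criterion while a Grade 2 cognitive effect or, more narrowly, intracranial bleed is ongoing

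*Protocol*

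**What the plan says.** Section 6.3.2 of the protocol lets either study drug return from a reduced dose to the level given immediately before "if any of the following criteria are met". In substance the three criteria are:

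1. Non-hematologic events of Grade 2 or higher, with CNS events expressly left out, have been below Grade 2 for at least 2 weeks.
2. Hematologic events of Grade 3 or higher are down to Grade 2 or less and manageable.
3. CNS events of Grade 2 or higher are down to Grade 1 or less and manageable.

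Further steps, up to 300 mg for avapritinib, are allowed "if the above criteria continue to be met".

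Table 1 governs avapritinib dosing after CNS events. After a Grade 2 cognitive or mood effect, dosing resumes 100 mg lower "when the cognitive effect has improved to Grade 1 or less, or still at Grade 2", the latter if treatment is judged in the patient's interest. After a Grade 3-4 effect it may resume 100 mg lower at Grade 1 or less, "or when it has improved to Grade 2, if continued treatment is considered in the best medical interest of the patient". After a Grade 2 intracranial bleed it resumes 100 mg lower "when the intracranial bleeding has improved to Grade 1 or less, or still at Grade 2", with the same best-interest condition. A Grade 2 bleed at 100 mg, and any Grade 3-4 bleed, means discontinuation.

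Section 6.3.1 introduces the re-escalation rule: "Once adverse drug reactions have resolved after the guidelines below are followed, Investigators are encouraged to re-escalate the dose of study drug", and points to 6.3.2 for how.

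**The concern.** The authors wrote a separate and stricter recovery threshold for CNS toxicity, Grade 1 or less. The word joining the three criteria means that this threshold need not be met. A patient whose dose was cut for a cognitive effect that persists at Grade 2 can qualify to go back up because a rash or a neutropenia has recovered.

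These are the events the documents single out. Cognitive effects and intracranial bleeding are the two categories of adverse events of special interest in SAP 4.7.2. Every intracranial bleed is reportable as serious under Protocol 9.1.3. CNS effects including brain hemorrhage were dose limiting in dogs (Protocol 1.2.2.3). What is at stake is patient safety and uniform conduct across sites, not the statistical inference.

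**Working it through.** No statistical figure is involved, so the check sets the rules side by side.

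**Step 1. Is the situation reachable?** Yes, under Table 1. A patient on 300 mg develops Grade 2 memory impairment. Dosing is interrupted for at least 7 days and resumes at 200 mg with the effect still at Grade 2. Later a Grade 2 rash appears, for which the General rows require no dose change, and it stays below Grade 2 for 2 weeks.

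**Step 2. Apply 6.3.2.** If the patient has no other non-hematologic event of Grade 2 or higher outside the CNS, criterion 1 is met. Criterion 3 is not met. One criterion is enough, so a return to 300 mg is literally permitted.

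**Step 3. Generalize.** Hold criterion 3 as unmet and vary the other two:

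| Criterion 1 | Criterion 2 | Any one suffices | All required |
|---|---|---|---|
| met | met | permitted | barred |
| met | unmet | permitted | barred |
| unmet | met | permitted | barred |
| unmet | unmet | barred | barred |

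The current wording permits the step in 3 of 4 combinations. Requiring all three permits it in 0 of 4.

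**Step 4. Size of one step.** Section 1.2.3.1 states that "systemic exposure was dose proportional over the dose range of 30 mg to 400 mg QD". On that basis, 200 to 300 mg gives 300/200 − 1 = +50% exposure, and 100 to 200 mg gives 200/100 − 1 = +100%. As a rough check on the reported steady-state means at 300 and 400 mg, the AUC ratio is 20298/14074 = 1.44 and the Cmax ratio is 1009/774 = 1.30, against a dose ratio of 400/300 = 1.33.

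**Step 5. Does other text close the gap?**

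- *The 6.3.2 heading and the 6.3.1 sentence.* Both speak of resolution, but neither states a grade for CNS events. Section 6.3.1 itself treats a toxicity as resolved enough to resume dosing at Grade 2 or less, so the word does not exclude a persisting Grade 2 event.
- *Table 1, footnote 2.* After a cognitive, mood or bleeding event, "the investigator must document in writing that resuming avapritinib treatment was considered to be in the best medical interest of the patient". This covers resuming, not raising the dose afterwards.
- *Deviation reporting in 6.3.1.* Departures from the dose guidelines must be documented and sent to the sponsor. A step that satisfies 6.3.2 as written is not clearly a departure.
- *Later steps.* The wording quoted for them drops the word any and refers to the criteria in the plural. This may be meant as all three, but it does not govern the first step.

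**The case against.** The strongest reply is that no sensible investigator would read the rule this way. The heading and 6.3.1 tie re-escalation to resolution. Table 1 has just required a reduction for the CNS event, and reversing it while the event persists would defeat that instruction. The natural reading is that the criterion for the toxicity behind the reduction applies. Re-escalation is optional, 6.3.1 leaves room for clinical judgment, and the ceiling is the 300 mg starting dose, below the 400 mg maximum tolerated dose. No dose-limiting toxicity was seen from 30 to 400 mg in Phase 1.

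Much of this stands. The literal result was almost certainly not intended, and the dose never exceeds one already judged acceptable as a starting dose. But the starting dose is not the right comparison for a patient who has just had a CNS event on it. The operative sentence still says the opposite of the apparent intent.

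Three stronger readings are tempting and not supported:

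- *A reader might infer that almost any patient reduced first for, say, Grade 3 anemia and then for a cognitive effect could reverse the second reduction at once.* Table 1 normally requires the anemia to be at Grade 2 or less, or back to baseline, before dosing resumes after the first reduction. Its recovery would therefore usually be no new trigger. Reading it as one would empty the CNS reduction of effect.
- *A reader might count the paths through Table 1 as a measure of risk.* Such a count would miss other CNS events handled under the General rows and would say nothing about frequency.
- *A reader might extend the point to regorafenib, because Appendix 2 and 6.3.2 set different recovery grades.* That is a separate matter. Aligning to Appendix 2 would loosen a control-arm rule without a safety reason.

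**Conclusion.** The point holds as a drafting defect in a safety rule. On the first step, 6.3.2 literally permits going up one avapritinib level while the CNS criterion is unmet, and Table 1 makes that situation reachable. The bleeding case is narrow: only a Grade 2 bleed that began above 100 mg and is still at Grade 2 when dosing resumes.

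The size per patient is one dose level, about +50% or +100% exposure if dose proportionality holds, capped at 300 mg. The number of patients cannot be estimated. Phase 1 reports cognitive effects in 30% and anemia in 31% of patients, but gives no joint frequency and no count of persisting Grade 2 CNS events. The documents do not support a claim that patients have been or will be harmed, or that the sponsor chose this policy.

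The conclusion assumes that Table 1, whose title also mentions re-escalation, carries no re-escalation condition beyond the text available here. No endpoint, alpha or power is affected.

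**What to change.** In 6.3.2, replace "if any of the following criteria are met" with: *if all applicable criteria below are met, that is, the criterion for each toxicity class that led to a dose reduction*. Use the same wording for later steps in place of "if the above criteria continue to be met".

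Then add: *Avapritinib is not re-escalated while a cognitive or mood effect or intracranial bleed of Grade 2 or higher is ongoing.* The added sentence is needed because Table 1 lets a patient already at 100 mg resume at 100 mg with a Grade 2 cognitive effect. That event led to no reduction, so the class-based wording alone would not catch it. Limiting the sentence to these two event types avoids barring patients for other Grade 2 CNS events, for which the General rows require no dose change.

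Appendix 2 stays as it is.

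The cost is a wording change in the next amendment and a notice to sites. The downside is that a few patients with persisting Grade 2 CNS effects stay longer at the reduced dose.
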